6.12.4. Clinical Laboratory Evaluation

Clinical laboratory assessments include hematology, serum chemistry, urinalysis, and safety-related immune markers such as neutrophil counts.

Continuous laboratory tests will be summarized as changes from baseline to last observation for patients who have both baseline and at least one postbaseline result for Period 2 and 3, respectively:

- The scheduled visits/measurements will be included. The unscheduled visits and the repeat measurements will be excluded.
- Both international system of unit (SI) and conventional unit will be summarized when different.
- For the Safety Population for Period 2, the comparisons between and among treatment group will be conducted using an ANCOVA with treatment group and baseline value in the model.
- Data will be analyzed based on original scale.

Laboratory test observed values at each visit (starting at baseline) and change from baseline to each scheduled visit, respectively, will be displayed in box plots for patients who have both a baseline and at least one postbaseline result. These box plots will be used to evaluate trends over time and to assess a potential impact of outliers on central tendency summaries.

- The scheduled visits/measurements will be included. The unscheduled visits and the repeat measurements will be excluded.
- The displays with both SI and conventional units will be provided when different.
- The following summary statistics will be included as a table below the box plot: number of patients with a baseline and at least one postbaseline result, mean, standard deviation, minimum, Q1, median, Q3, and maximum.
- Data will be summarized based on original scale.
- On the box plots of the laboratory test observed values, the lines of the reference ranges/limits (by using the performing laboratory reference ranges) will be added. In cases where limits vary across age and gender, the lowest of the high limits and the highest of the low limits will be used.

The number and percentage of patients with a treatment-emergent or follow-up emergent abnormal, high, or low for laboratory tests will be summarized by treatment group for each study period (Period 2 or 3 or 4). The comparisons between and among treatment groups will be conducted using Fisher's exact test for the Safety Population for Period 2.

- All scheduled, unscheduled and repeated measurements will be included.
- Performing laboratory will be used to defined the low and high limits reference ranges except for leukocyte, neutrophil, lymphocyte and platelet counts, where Lilly defined lower limit of normal will be used for these 4 labs.
- Alanine aminotransferase (ALT), aspartate aminotransferase (AST), total bilirubin, alkaline phosphatase (ALP), neutrophils, leukocytes, platelets, and lymphocytes will not

be included in the treatment-emergent abnormal, high, or low summary as a separate analysis addressing the risk of liver injury is described in Section 6.12.3.1 and a separate analysis addressing Leukocytes (WBC) and Platelets is described in Section 6.12.4.1.

- Note that the ranges are defined by a lower limit of normal (LLN) and an upper limit of normal (ULN). A result that is greater than or equal to the LLN and less than or equal to the ULN is considered to be within the normal ranges.
- For categorical laboratory tests:
 - Treatment-emergent abnormal value is defined as a change from normal at all baseline visits to abnormal at any time postbaseline during the treatment period.
 - Follow-up emergent abnormal result is defined as a change from normal at baseline to abnormal at any time during the follow-up period.
- For continuous laboratory tests:
 - Treatment-emergent high value is defined as a change from a value less than or equal to the ULN at all baseline visits to a value greater than the ULN at any time postbaseline during the treatment period.
 - Treatment-emergent low value is defined as a change from a value greater than or equal to the LLN at all baseline visits to a value less than the LLN at any time postbaseline during the treatment period.
 - Follow-up emergent high value is defined as a change from a value less than or equal to the ULN at baseline to a value greater than the ULN at any time postbaseline during the follow-up period.
 - Follow-up emergent low value is defined as a change from a value greater than or equal to the LLN at baseline to a value less than the LLN at any time postbaseline during the follow-up period.

By-patient listing of laboratory test values will be provided. Listing of laboratory tests reference ranges (Lilly defined lower limit of normal for leukocyte, neutrophil, lymphocyte and platelet counts and Performing Lab reference ranges for other lab tests) will be provided. By-patient listing of abnormal laboratory test results (criteria defined in the shift tables excluding the normal category) for parameters of special interest (hepatic, leukocytes and platelets) will be provided.

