- t Only for females of childbearing potential. Serum pregnancy test will be done at Visit 1 only, and will be performed centrally. Patients determined to be pregnant will be discontinued from treatment and will no longer be administered investigational product (see Section 7.1). Patients will undergo urine pregnancy testing at the clinic during scheduled visits through Week 52. Additional urine pregnancy testing can be performed at the investigator's discretion. If required per local regulations, testing can occur at other intervals during the study treatment period and/or follow up period. Patients determined to be pregnant will be discontinued from treatment and will no longer be administered investigational product (see Section 7.1).
- u For the fasting lipid profile patients are not to eat or drink anything except water for 12 hours prior to test.
- v Where collection is allowed by local regulations.
- w Only serum and plasma are collected at this visit.
- x Immunogenicity samples may also be analyzed for ixekizumab serum concentration to facilitate in the interpretation of immunogenicity data. An additional blood sample will be collected, when possible, for any patient who experiences a potential systemic allergic/hypersensitivity reaction during the study as judged by the investigator.
- y PK samples are to be collected before investigational product injection.
- z The Week 52 MRI may be collected up to 10 days **prior** to Week 52 (Visit 15).

- aa Patients receiving investigational product who discontinue at any time prior to the end of the study or who complete the study (Week 52) and do not choose to enroll in Study RHBV, will have safety Follow-Up Visits 801 and 802 at 4 and 12 weeks (respectively) after the date of their last visit. Visit 803 will occur if a patient's neutrophil counts have not returned to the criteria defined in Section [8.4.10.1](#).
- bb Weight is only captured on eCRF at V2, V8, V10, V15, and/or ETV. Body weight collected at other visits is used only for calculation of creatinine clearance.
- cc If not completed at Visit 2, the sample should be collected as soon as possible at the next scheduled visit.

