### Clinical Safety Laboratory Tests to be Performed by Sponsor-Designated Laboratory

Hematology a :	Serum Chemistry a :
Hemoglobin	Sodium
Hematocrit	Potassium
Erythrocyte count (RBC)	Bicarbonate
Mean cell volume (MCV)	Chloride
Mean cell hemoglobin concentration (MCHC)	Phosphorus
Leukocytes (WBC)	Total bilirubin
Platelets	Direct bilirubin
Absolute counts of:	Alkaline phosphatase
Neutrophils, segmented	Alanine aminotransferase (ALT/SGPT)
Neutrophils, juvenile (bands)	Aspartate aminotransferase (AST/SGOT)
Lymphocytes	Blood urea nitrogen (BUN)
Monocytes	Uric acid
Eosinophils	Creatinine
Basophils	Calcium
Urinalysis (dipstick)a:	Glucose
Color	Albumin
Specific gravity	Cholesterol (total)
pH	Total protein
Protein	Calculated creatinine clearance b
Glucose	Creatine phosphokinase (CPK)
Ketones	Triglycerides
Bilirubin	Gamma-glutamyl transferase (GGT)
Urobilinogen	
Blood	Lipid panelc
Nitrite	Low density lipoprotein (LDL)
Urine creatinine	High density lipoprotein (HDL)
Leukocyte esterase	Very low density lipoprotein (VLDL)
Other Tests:	
Human immunodeficiency virus antibody (HIV) f	Pregnancy test (serum) d
Hepatitis B surface antigen (HBsAg) f	Follicle-stimulating hormone (FSH) e
Anti-hepatitis B surface antibody (HBsAb) f	Thyroid-stimulating hormone (TSH) and free T4
Anti-hepatitis B core antibody (HBcAb) f	Ixekizumab serum concentration (pharmacokinetic)
Anti-hepatitis C antibody f,h	Partial thromboplastin time (PTT)
HBV DNA g	Prothrombin time/international normalized ratio
High sensitivity C-reactive protein (CRP)	Exploratory storage samples (urine, serum, plasma, RNA, and whole blood)
Purified protein derivative (PPD) i	Pharmacogenetic sample (DNA)
Urine pregnancy test d (assayed by clinical study site)	Immunogenicity testing (anti-ixekizumab Ab)
QuantiFERON®-TB Gold test i	
T-SPOT® i	
HLA-B27	

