**Clinical Safety Laboratory Tests**

Abbreviations: Ab = antibody; DNA = deoxyribonucleic acid; HBV = hepatitis B virus; RNA = ribonucleic acid; RBC = red blood cells; SGOT = serum glutamic oxaloacetic transaminase; SGPT = serum glutamic pyruvic transaminase; T4 = thyroxine; WBC = white blood cells.

- a Unscheduled blood chemistry, hematology, and urinalysis panels may be performed at the discretion of the investigator.
- b Cockcroft-Gault calculation is used for the calculated creatinine clearance.
- c For the fasting lipid profile, patients are not to eat or drink anything except water for 12 hours prior to test. Fasting is not required for the screening visit (Visit 1).
- d Serum pregnancy test for all women <60 years of age who are still of childbearing potential at Visit 1 only and will be performed centrally; after Visit 1, urine pregnancy test performed locally for women of childbearing potential.
- e Women  $\geq 40$  and <60 years of age who have had a cessation of menses for  $\geq 12$  months will have an FSH test confirming nonchildbearing potential ( $\geq 40$  mIU/mL).
- f Test required at Visit 1 to determine eligibility of patient for the study.
- g HBV DNA testing will be done in those patients who are HBcAb+ at screening.
- h See exclusion criteria (Section 5.2) specific to Hepatitis C antibody. A confirmatory test for HCV will be performed if the patient is positive for HCV antibody.
- i In countries where the QuantiFERON®-TB Gold test or T-SPOT® is available, either test may be used instead of the PPD TB test. The QuantiFERON®-TB Gold test may be performed locally or centrally; the T-SPOT® must be performed locally.

---

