6.1.2. General Considerations for Analyses during the Extended Treatment Period (Period 3)

Unless otherwise specified, Period 3 starts at the first injection of study treatment at Week 16 (Visit 8) and ends on the date of Week 52 (Visit 15) or the ETV (between Weeks 16 and 52).

For the efficacy and health outcome analyses, baseline is defined as the last available value before the first injection in Period 2 and, in most cases, will be the value recorded at Week 0 (Visit 2).

Unless otherwise specified, for the safety analyses during Period 3, baseline is defined as the last available value before first injection of ixekizumab in Period 3. In most cases, this will be the measure recorded at Week 16 (Visit 8). For adalimumab patients in Period 2 who are randomized to ixekizumab during Period 3, this will be the measure recorded at Week 20 (Visit 9). For treatment-emergent adverse events (TEAEs), baseline is the events ongoing just prior to the first injection of the study drug injection at Week 16 (for placebo and ixekizumab patients) or Week 20 (for adalimumab patients who are randomized to ixekizumab during Period 3).

The number and percentage of patients having categorical efficacy response (for example, ASAS40) will be summarized by treatment group for all scheduled visits (NRI), including Week 52 (Visit 15) during Period 3.

In addition, the number and percentage of patients achieving response on ASAS20 for those who did not achieve response at Week 16, and the number and percentage of patients maintaining response for those who achieved response at Week 16, will be summarized by treatment group for all scheduled visits (NRI), including Week 52 (Visit 15) during Period 3. Similar summary will be provided for ASAS40.

Each continuous efficacy and health outcome score and change from baseline (or percent improvement) will be summarized by treatment group at all scheduled visits, including Week 52 (Visit 15) using descriptive statistics (n, mean, SD, median, minimum and maximum). Missing data will be imputed using mBOCF method (Section 6.3.2).

The categorical safety measures will be summarized with incidence rates. The mean change of the continuous safety measures will be summarized at all scheduled visits.

6.1.3. General Considerations for Analyses during Combined Blinded Treatment Dosing Period and Extended Treatment Period (Combined Periods 2 and 3)

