6.12. Safety Analyses

Safety will be assessed by summarizing and analyzing AEs, laboratory analytes, vital signs, QIDS-SR16, and C-SSRS. The duration of treatment exposure will also be summarized.

For **Period 2**, safety data will be summarized for the safety population. Treatment group comparisons will be performed on categorical safety data using Fisher's exact test as described in Section 6.1.1, continuous safety data will be analyzed by an ANCOVA model as described in Section 6.1.1.

For **Period 3**, safety data will be summarized for the Extended Treatment Period Population and no treatment group comparisons will be performed.

For Combined Periods 2 and 3, safety data will be summarized for the Safety Population who are initially randomized to Ixekizumab, and no treatment group comparisons will be performed. In addition, safety data on ixekizumab will be summarized for All Ixekizumab Exposures Safety Population who had at least 1 dose of Ixekizumab.

For **Period 4**, safety data will be summarized according to the treatment patients were on or prior to entering Post-Treatment Follow-up Period.

For safety analyses, the following baselines will be used:

- Treatment-emergent adverse events (TEAEs): baseline will be all results recorded during the baseline period (see Section 6.1 for definitions of the baseline period).
- Change from baseline to last observation and each scheduled postbaseline visit for laboratory and vital signs: baseline will be last non-missing assessment recorded during the baseline period (see Section 6.1 for definitions of the baseline period).
- Treatment-emergent abnormal laboratory and vital signs: baseline will be all results recorded during the baseline period (see Section 6.1 for definitions of the baseline period).
- Change from baseline to minimum or maximum: baseline will be all results recorded during the baseline period (see Section 6.1 for definitions of the baseline period).

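### The laboratory summaries pool fasting-visit and non-fasting-visit triglycerides, glucose and total cholesterol, which can distort the uncontrolled Period 3 rates and mean changes

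*SAP*

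**What the plan says.** **Which samples count.** SAP 6.12.4, on treatment-emergent and follow-up emergent abnormal values, says "All scheduled, unscheduled and repeated measurements will be included". The only analytes it takes out are liver tests and blood counts: "Alanine aminotransferase (ALT), aspartate aminotransferase (AST), total bilirubin, alkaline phosphatase (ALP), neutrophils, leukocytes, platelets, and lymphocytes will not" be part of that summary, because they are analysed elsewhere. Triglycerides, glucose and total cholesterol stay in. No fasting flag or visit restriction appears.

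**Where these analytes sit.** Protocol Appendix 3 lists "Triglycerides", glucose and total cholesterol under serum chemistry. Its lipid panel holds only LDL, HDL and VLDL.

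**When a fast is required.** The Schedule of Activities footnote reads "For the fasting lipid profile patients are not to eat or drink anything except water for 12 hours prior to test". The fasting lipid panel is scheduled at V2, V8 (Week 16), V10 (Week 24), V13 (Week 36) and V15 (Week 52). Appendix 3 adds "Fasting is not required for the screening visit (Visit 1").

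**Baselines.**
- SAP 6.12.4: "Treatment-emergent high value is defined as a change from a value less than or equal to the ULN at all baseline visits", followed by a value above the ULN at any later time in the period.
- SAP 6.12: "Treatment-emergent abnormal laboratory and vital signs: baseline will be all results recorded during the baseline period". For Period 2, SAP 6.1.1 starts that period at Visit 1.
- SAP 6.1.2: the Period 3 safety baseline is the last value before the first Period 3 ixekizumab injection, in most cases Week 16. For adalimumab patients "this will be the measure recorded at Week 20 (Visit 9").
- SAP 6.1.4: the Period 4 baseline is the last value on or before Week 52 or the early termination visit (ETV).

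**The concern.** Triglycerides, and to differing degrees glucose and total cholesterol, may depend on whether the patient has eaten. A value that is normal after a 12-hour fast and high at a visit with no fast enters the table as treatment-emergent high, whatever the drug does.

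A concurrent arm on the same schedule would show the same effect, and the reader could subtract it. SAP Table RHBV.6.2 plans no between-group comparisons in Periods 3 and 4, and every Period 3 patient is on ixekizumab. A raised rate there could be read as a metabolic signal of the drug.

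The Period 3 groups also differ in the direction of the distortion. The pooled Total Ixekizumab Q4W and Q2W groups (Table RHBV.6.2, footnote c) combine adalimumab switchers with patients from placebo and ixekizumab, and so mix the two patterns.

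**Working it through.** The plan gives no figure on this point, so there is nothing to reproduce. The check has two parts: set the chemistry visits against the fasting visits, then illustrate the size.

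**Step 1. Visits (Protocol Appendix 2; baselines from SAP 6.1.1, 6.1.2, 6.1.4 and 6.12).**

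| Comparison | Baseline | Scheduled postbaseline chemistry | No fast required |
|---|---|---|---|
| Period 2, all arms | V1 (no fast) and V2 (fast) | W4, W8, W12, W16 | 3 of 4 (W4, W8, W12) |
| Period 3, from placebo or ixekizumab | W16 (fast) | W20, W24, W28, W32, W36, W44, W52 | 4 of 7 (W20, W28, W32, W44) |
| Period 3, from adalimumab | W20 (no fast) | W24, W28, W32, W36, W44, W52 | 3 of 6 (W28, W32, W44) |
| Period 4, completers | W52 (fast) | V801, V802 | all |
| Period 4, from ETV | ETV (no fast) | V801, V802 | all |

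**Step 2. Model for triglycerides (all inputs assumed).** Fasting values are log-normal with median 110 mg/dL. On the log scale the between-patient SD is 0.45 and the within-patient SD 0.25. There is no drug effect. Values at visits without a required fast are higher by a shift *s* of 10% to 30%. The ULN is 150 mg/dL, or 200 as an alternative.

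For a patient with log mean μ, let f = Φ[(ln ULN − μ)/0.25] be the chance that a fasting sample is at or below the ULN. Let u = Φ[(ln ULN − μ − ln(1+s))/0.25] be the same for a non-fasting sample. With E the average over patients, the treatment-emergent high rate is:

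- Period 3, from placebo or ixekizumab: 1 − E[f⁴u⁴]/E[f] (baseline f, three later f, four u).
- Same visits, no meal effect: 1 − E[f⁸]/E[f].
- Fasting visits only: 1 − E[f⁴]/E[f].
- Adalimumab switchers: 1 − E[u⁴f³]/E[u].
- Period 4 completers, V801 and V802: 1 − E[f u²]/E[f]. From ETV: 1 − E[u³]/E[u].
- Period 2: 1 − E[u⁴f²]/E[u f]. The V1 sample supplies one u in the numerator and the u in the denominator.

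**Step 3. Results (simulation of 400,000 patients per scenario).**

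| Quantity | s = 10% to 30% | s = 0 |
|---|---|---|
| Period 3, placebo or ixekizumab, ULN 150 | 43% to 56% | 36.5% |
| Period 3, placebo or ixekizumab, ULN 200 | 26% to 37% | 21% |
| Adalimumab switchers, ULN 150 | 36% to 40% | 34% |
| Period 4 completers, ULN 150 | 28% to 43% | 20% |
| Period 4 from ETV, ULN 150 | 24% to 32% | 20% |
| Period 2 including V1, ULN 150 | 26% to 35% | 22% |

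The meal effect is the gap between the two columns: about 6 to 20 points in the first row. With fasting visits only, the Period 3 rate is 25% (ULN 150) or 13% (ULN 200). The drop from 36.5% to 25% occurs with no meal effect at all, because three later samples replace seven.

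**Step 4. Switchers' mean change.** From Week 20 (no fast) to Week 52 (fast) with no drug effect, the ratio is 1/(1+s): 1/1.10 − 1 = −9% and 1/1.30 − 1 = −23%.

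**Step 5. Period 2 test.** Suppose each non-fasting sample is high with probability q, independently, in every arm. The meal-driven rate over three samples is 1 − (1−q)³: 14%, 27% and 49% for q = 5%, 10% and 20%. Enumerating Fisher's exact test at 80 per arm with these equal rates gives a type I error of 0.030 to 0.033, which is not inflated.

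**The case against.** The strongest reply concerns Period 2, the only period with formal tests. A reader might infer that a fasting baseline there is set against unfasted later samples, so that meals count against the drug. The documents do not support this. The rule requires normal values at all baseline visits, and those include V1, where no fast is required. Under the model, using V1 lowers the Period 2 rate from 36-51% to 26-35%. Every arm, placebo included, follows one schedule. This part of the reply stands in full.

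Other points also stand:

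- The protocol says where a fast is required. It does not say that patients ate at the other visits, and treatment-emergent is a label of timing, not of cause.
- The median, SDs, shift and ULN are assumptions; the SAP uses the performing laboratory's limits. Only triglycerides are modelled. The documents support no size for glucose or total cholesterol.
- Comparing 43-56% with 25% would mix the meal effect with the number of visits.
- A reader might extend the Period 4 point to everyone. Patients entering from an ETV have non-fasting samples on both sides.
- Neither lipids nor glucose is an adverse event of special interest. The per-visit box plots with their summary tables, and the listings, let a careful reader find the fasting visits.

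That last point reduces the problem without removing it. The incidence table is not split by visit, and the change plots for switchers still start from Week 20.

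A fasting-only replacement would itself do harm. It would leave one of four scheduled postbaseline samples in Period 2, drop patients who stop before Week 16 (the ETV has no lipid panel), and lose unscheduled and repeat values from a safety table.

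**Conclusion.** The concern holds for Period 3 and for completers entering Period 4. Pooling without regard to fasting leaves crude rates that cannot be separated from meals, and no control arm is there to show the difference. For triglycerides in patients from placebo or ixekizumab, the illustrative Period 3 rate is 43-56% against 36.5% on the same visits with no meal effect (ULN 150). The switchers' mean change is lowered by 9-23%. These sizes rest wholly on the assumed distribution, ULN and shift; the direction rests on the schedule and on the assumption that some patients are unfasted when no fast is required.

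In Period 2 the effect is noise common to all arms, partly screened out by V1, and not bias toward ixekizumab. The primary and major secondary efficacy analyses are untouched. This is a worthwhile, low-cost correction to a safety table.

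**What to change.** In SAP 6.12.4, for triglycerides, glucose and total cholesterol:

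1. Keep the planned all-sample summary, labelled as mixed fasting status.
2. Add a tabulation of treatment-emergent high and low values and of mean change limited to fasting visits. Use V2 as the Period 2 baseline with V8 postbaseline, and V8 as the Period 3 baseline with V10, V13 and V15 postbaseline.
3. In that added table only, use Week 16 for adalimumab switchers, as their last fasting-visit value before ixekizumab. Note that the interval then includes the Week 16-20 washout. The Week 20 baseline in SAP 6.1.2 stays for all other safety analyses.
4. Label the follow-up emergent results for these analytes as non-fasting.

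The cost is one extra table and a visit filter, with no new data collection. The fasting-only version has fewer samples and no ETV values, which is why it should stand beside the planned summary and not replace it.
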